8.0 TRIAL PROCEDURES

8.1 Trial Procedures

The Trial Flow Chart - Section 7.0 summarizes the trial procedures to be performed at each visit. Individual trial procedures are described in detail below. It may be necessary to perform these procedures at unscheduled time points if deemed clinically necessary by the investigator.

Furthermore, additional evaluations/testing may be deemed necessary by the Sponsor for reasons related to subject safety. In some cases, such evaluation/testing may be potentially sensitive in nature (e.g., HIV, Hepatitis C, etc.), and thus local regulations may require that additional informed consent be obtained from the subject. In these cases, such evaluations/testing will be performed in accordance with those regulations.

8.1.1 Administrative Procedures

8.1.1.1 Informed Consent

The Investigator must obtain documented consent from each potential subject prior to participating in a clinical trial.

The principles of informed consent are described by Federal Regulatory Guidelines (Code of Federal Regulations, Title 21, Volume 1, Part 50, Revised April 1, 2013) and the Office for Human Research Protections (Code of Federal Regulations 45 CFR 46). They must be followed to comply with federal regulations for the conduct and monitoring of clinical investigations.

8.1.1.1.1 General Informed Consent

Consent must be documented by the subject's dated signature or by the subject's legally acceptable representative's dated signature on a consent form along with the dated signature of the person conducting the consent discussion. The case history for each subject shall document that informed consent was obtained prior to participation in the study and before any study related procedure(s) was performed. Original signed consent forms must be filed in the site study binder or in each subject's study file.

A copy of the signed and dated consent form should be given to the subject before participation in the trial.

The initial informed consent form, any subsequent revised written informed consent form and any written information provided to the subject must receive the IRB/ERC's approval/favorable opinion in advance of use. The subject or his/her legally acceptable representative should be informed in a timely manner if new information becomes available that may be relevant to the subject's willingness to continue participation in the trial. The communication of this information will be provided and documented via a revised consent

Product: MK-3475

Protocol/Amendment No.: Amendment 5, 21 October 2019

form or addendum to the original consent form that captures the subject's dated signature or by the subject's legally acceptable representative's dated signature.

Specifics about a trial and the trial population will be added to the consent form template at the protocol level.

The informed consent will adhere to IRB/ERC requirements, applicable laws and regulations and Sponsor requirements.

8.1.1.2 Inclusion/Exclusion Criteria

All inclusion and exclusion criteria will be reviewed by the Investigator or qualified designee to ensure that the subject qualifies for the trial.

8.1.1.3 Subject Identification Card

All subjects will be given a Subject Identification Card identifying them as participants in a research trial. The card will contain trial site contact information (including direct telephone numbers) to be utilized in the event of an emergency. The Investigator or qualified designee will provide the subject with a Subject Identification Card after the subject provides written informed consent.

8.1.1.4 Medical History/Demographics

A medical history will be obtained by the Investigator or qualified designee who is participating in the study (qualified physician or nurse practitioner listed as associated study personnel). Medical history will include demographics, height, and weight, and all active conditions, and any condition diagnosed within the prior 10 years that is considered to be clinically significant by the Investigator. History will also include the past and current use of alcohol, tobacco, and other illicit drugs and performance status as assessed by the ECOG scale (Appendix A). Details regarding the disease for which the subject has enrolled in this study will be recorded separately and not listed as medical history. Appropriate data will be captured in the CRF while all other data will be recorded in the source documents.

8.1.1.5 Prior and Concomitant Medications Review

8.1.1.5.1 Prior Medications

The Investigator or qualified designee will review prior medication use, including any protocol-specified washout requirement, and record prior medication taken by the subject within 28 days before starting the trial. Prior medications will include prescription, over the counter, and herbal/alternative therapies. Treatment for the disease for which the subject has enrolled in this study will be recorded separately and not listed as a prior medication.

Product: MK-3475

Protocol/Amendment No.: Amendment 5, 21 October 2019

8.1.1.5.2 Concomitant Medications

The Investigator or qualified designee will record medications, if any, taken by the subject during the trial. All medications related to reportable SAEs and ECIs should be recorded as defined in Section 9. Concomitant medications must be reviewed with the prohibited medications list to ensure patient safety.

8.1.1.5.3 Questionnaires

The American Urologic Association Symptoms Index and the Quality of Life Questionnaires (Appendix D) will be administered as outlined in Section 7. Subjects will be provided time and space to complete the questionnaires. A study coordinator will be on hand for any questions the subject may have. All answers will remain confidential and subjects will be instructed to answer all questions as honestly and completely as possible.

8.1.1.6 Disease Details and Treatments

8.1.1.6.1 Disease Details

The Investigator or qualified designee will obtain prior and current details regarding disease status. Disease details include, but are not necessarily limited to, symptoms associated with the disease, pathological and laboratory reports, imaging reports, treatments and response to treatments.

8.1.1.6.2 Prior Treatment Details

The Investigator or qualified designee will review all prior cancer treatments including systemic treatments, radiation and surgeries.

8.1.1.6.3 Subsequent Anti-Cancer Therapy Status

The Investigator or qualified designee will review all new anti-neoplastic therapy/treatment initiated after the last dose of trial treatment. If a subject initiates a new anti-cancer therapy/treatment within 30 days after the last dose of trial treatment, the 30 day Safety Follow-up Visit must occur before the first dose of the new therapy. Once new anti-cancer therapy has been initiated, the subject will move into survival follow-up at 3, 6, 9, 12, 18, and 24 months post treatment visits.

8.1.1.7 Assignment of Screening Number

Eligible subjects will be approached by consenting providers or research nurse to participate in this study. Subjects who do not meet the pathological criteria for enrollment will be considered a screen fail. Those subjects who meet pathological inclusion/exclusion criteria will be fully screened for other tests and procedures. Subjects will be assigned a 5-6 character ID code with the first three or four being the site code (a letter site code assigned to the site by the Sponsor) followed by a two digit number for a subject identifier beginning with 01 and each newly enrolled subject the subsequent number for that site. For example, SCI-03 would

Product: MK-3475

Protocol/Amendment No.: Amendment 5, 21 October 2019

represent the third patient enrolled at site SCI. Assigned subject numbers will only be used once. If a patient should be a screen failure, that number will be resigned and the next patient assigned the sequential number until enrollment is met. If a subject receives any part of the investigation treatment design and must discontinue treatment for any reason, they will not be replaced.

To register a subject, the following documents must be on file with the research nurse or data manager:

- Signed subject consent/HIPAA authorization form
- Copy of required laboratory test results
- Copy of the pathology report confirming high risk superficial transitional cell carcinoma histology
- Copy of the most recent history and physical dictation/record
- Any other documentation needed to verify inclusion/ exclusion criteria

The research nurse or data manager will verify eligibility with the Principal Investigator. To complete the registration process, the Project Manager will:

- Assign a subject study number
- Register the subject on the study

8.1.1.8 Trial Compliance

Subjects who, in the opinion of the treating Investigator and study staff, would not be compliant with study procedures and requirements should not be enrolled in the study. Patients who “no show” for more than 1 required visit for non-emergent or non-health related events may be considered non-compliant and discontinued from the study at the discretion of the treating Investigator.

8.1.2 Clinical Procedures/Assessments

Subjects diagnosed with T1 and Ta tumors require restaging after failure of BCG and one course of maintenance or failure after BCG plus one of the following: mitomycin, gemcitabine, or BCG/interferon. Subjects receiving bladder tumor resection at outside institutions are eligible for the study; however, pathology slides must be reviewed by the site’s pathology department. Each subject will receive a total of 6 cycles of treatment with MK-3475 at a dose of 100 (first 3 subjects) or 200 mg on Day 1 of a 21 day cycle. Two cycles of MK-3475 will occur prior to BCG intravesical treatment (weekly doses for 6 weeks) with concurrent treatment (MK-3475 and BCG) starting on cycle 3 and ending the third week of cycle 4. MK-3475 will then be continued as a single agent for 2 additional cycles after the last dose of BCG was administered.

8.1.2.1 Transurethral Resection of Tumor

Transurethral resection of bladder tumor is routine care for this population. Generally superficial bladder cancer subjects have 2 such resections as routine care prior to initial BCG therapy. The first generally occurs after cystoscopy and confirmation of malignancy via biopsy. The second generally occurs approximately 6 weeks following the first resection; however, timing may be extended if the subject is referred from an external clinic. A repeat resection may occur as part of restaging for recurrent/persistent disease after failed intervesical therapy to confirm pathology and cytology for localized high grade (G3) transitional cell carcinoma (urothelial carcinoma) of the bladder that is stage Ta, T1, and/or CIS.

8.1.2.2 Adverse Event (AE) Monitoring

The Investigator or qualified designee will assess each subject to evaluate for potential new or worsening AEs as specified in the Trial Flow Chart and more frequently, if clinically indicated. Adverse experiences will be graded and recorded throughout the study and during the follow-up period according to NCI CTCAE Version 4.0 (Appendix E). Toxicities will be characterized in terms regarding seriousness, causality, toxicity grading, and action taken with regard to trial treatment. AEs will be recorded from the time the subject signs the consent through 30 days post the last study treatment.

Please refer to section 9.0 for detailed information regarding the assessment and recording of AEs.

8.1.2.3 Full Physical Examination

The Investigator or qualified designee will perform a complete physical examination including vital signs (heart rate, blood pressure, temperature, respiratory rate) during the screening period. Clinically significant abnormal findings should be recorded as medical history. A full physical examination should be performed during screening and the 30 day Safety Visit.

8.1.2.4 Directed Physical Examination

For cycles that do not require a full physical examination per the Trial Flow Chart, the Investigator or qualified designee will perform a directed physical examination as clinically indicated prior to trial treatment administration. Directed physical examinations will also collect vital signs including heart rate, blood pressure, temperature, respiratory rate.

8.1.2.5 Vital Signs

The Investigator or qualified designee will take vital signs at screening, prior to the administration of each dose of trial treatment and at treatment discontinuation as specified in the Trial Flow Chart (Section 7.0). Vital signs should include temperature, pulse, respiratory rate, weight and blood pressure. Height will be measured at screening only.

Product: MK-3475

Protocol/Amendment No.: Amendment 5, 21 October 2019

8.1.2.6 Eastern Cooperative Oncology Group (ECOG) Performance Scale

The Investigator or qualified designee will assess ECOG status (Appendix A) at screening, prior to the administration of trial treatment at Week 7, Week 13, Week 19 and discontinuation of trial treatment or Safety Follow up visit as specified in the Trial Flow Chart.

8.1.2.7 Twelve-Lead Electrocardiograms (ECG)

During the screening period, a 12-lead ECG will be performed with the subject in a recumbent or semi-recumbent position after 5 minutes of rest. Interpretation may be by the Investigator or a qualified designee. ECGs completed within 90 days of the screening visit will be acceptable for the study, unless a suspected cardiac event has occurred in that 90 day period.

8.1.2.8 Chest X-Ray

A chest X-ray, both PA and lateral views, will occur at screening to confirm non-metastatic disease as well as to provide a baseline evaluation for pulmonary status. X-Rays completed within the 90 days prior to the screening visit are acceptable.

8.1.2.9 Pulmonary Function Tests (PFT)

Baseline PFTs will occur at screening to assess lung volume, capacity, rate of flow, and gas exchange. Throughout the course of the study, additional PFTs will be performed if clinically indicated. If DLCO decreases by greater than 10%, the subject will be considered to have interstitial lung disease if no other obvious reason for the decrease. The following will be collected:

- Vital Capacity (VC)
- Functional Residual Capacity (FRC)
- Total Lung Capacity
- Forced Vital Capacity (FVC)
- Forced Expiratory Volume (FEV)
- Forced Expiratory Flow (FEF)Peak Expiratory Flow Rate (PEFR)

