5.1.3 Subject Exclusion Criteria

The subject must be excluded from participating in the trial if the subject:

1. Currently has active or progressive metastatic disease. (Chest X-ray, Computerized Tomography [CT] urogram or Magnetic Resonance Imaging [MRI] and urogram are allowed to ascertain the superficial nature of the disease when indicated, but not required. If urogram protocol is not available or contrast allergy/poor renal function precludes such imaging, then non-contrast CT or MRI of the abdomen/pelvis within 90 days of study entry will suffice.)
2. Is currently participating in or has participated in a study of an investigational agent or using an investigational device within 4 weeks of the first dose of treatment.
3. Has a diagnosis of immunodeficiency or is receiving systemic steroid therapy or any other form of immunosuppressive therapy within 7 days prior to the first dose of trial treatment.
4. Has had a prior monoclonal antibody within 4 weeks before study Day 1 or who has not recovered (i.e., \leq Grade 1 or at baseline) from adverse events due to agents administered more than 4 weeks earlier.
5. Has had prior systemic chemotherapy, targeted small molecule therapy, or radiation therapy for bladder cancer.
6. If subject received major surgery, they must have recovered adequately from the toxicity and/or complications from the intervention prior to starting therapy.
7. Has a known additional malignancy that is progressing or requires active treatment. Exceptions include basal cell carcinoma of the skin, squamous cell carcinoma of the skin, or in situ cervical cancer that has undergone potentially curative therapy. Upper urinary

tract transitional cell carcinoma is also allowable on study as high risk transitional cell carcinoma is commonly multifocal, and intraluminal BCG therapy is also used for treatment of upper urinary tract lesions in a manner similar to that of bladder tumors.

8. Active autoimmune disease that has required systemic treatment in the past 2 years (i.e. with use of disease modifying agents, corticosteroids or immunosuppressive drugs). Replacement therapy (e.g. thyroxine, insulin, or physiologic corticosteroid replacement therapy for adrenal or pituitary insufficiency, etc.) is not considered a form of systemic treatment.
9. Has evidence of interstitial lung disease or active, non-infectious pneumonitis.
10. Has an active infection, including a concurrent febrile illness, requiring systemic therapy.

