8.1.6.1 Screening

8.1.6.1.1 Screening Period

The screening period covers the 90 days prior to Day 1, Cycle 1. Days –90 through –28 will include restaging for Ta and T1 tumors.

The study screening visit is mandatory and must occur in the 28 days prior to Day 1, Cycle 1 of treatment. The study screening visit includes full study informed consent and documentation of consent. No study required procedures (excluding those that are standard of care) are to occur prior to informed consent of the subject. All inclusion/exclusion criteria must be reviewed and all of the inclusion and none of the exclusion criteria must be met to advance the subject on to the Treatment Period. The screening period procedures include: full study informed consent, review of inclusion/exclusion criteria, documentation of demographics and medical history, concomitant medication review, cystoscopy and urine cytology, including restaging of tumor for Ta and T1, review of ongoing symptoms for documentation of baseline adverse effects, full physical examination, ECOG performance status, vital signs, electrocardiogram, chest X-ray, and baseline pulmonary function tests as well as laboratory assessments indicated in Section 7–Trial Flow Chart. Collection of a baseline bladder cancer tumor specimen, as well as baseline blood and urine specimens for correlative studies, will also occur during the screening period. Assessment of coagulation status will be performed prior to each resection as per standard of care.

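### The on-study interstitial lung disease rule uses a fall in DLCO, but DLCO is not among the lung function values to be collected, so its pre-treatment value is not secured

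*Combined protocol and SAP*

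**What the plan says.** Three statements in section 8.1.2.9 of the combined protocol and SAP bear on this.

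- Purpose: "Baseline PFTs will occur at screening to assess lung volume, capacity, rate of flow, and gas exchange".
- Rule: "If DLCO decreases by greater than 10%, the subject will be considered to have interstitial lung disease", unless something else plainly accounts for the fall.
- Collection list: VC, FRC, total lung capacity, FVC, FEV, FEF and PEFR. The last two run together on one line in the text supplied.

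On repeat testing the section says: "Throughout the course of the study, additional PFTs will be performed if clinically indicated". Footnote m of the flow chart (section 7.1) agrees: the tests are done before Day 1 of Cycle 1 and afterwards only on clinical indication. The screening section (8.1.6.1.1) calls for "chest X-ray, and baseline pulmonary function tests as well as laboratory assessments" without naming any components of the lung function tests.

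**The concern.** A rule defined as a percentage fall needs two values of the same variable: one before treatment and one after. The plan supplies the rule but does not list its variable among the data to be collected. If a subject develops respiratory symptoms during treatment and DLCO is measured then for the first time, there is nothing to compare it with. A pre-treatment measurement cannot be taken retrospectively.

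Safety of the combination is the primary objective (section 3.1), and this is the only numeric definition of interstitial lung disease in the protocol. If the baseline is missing, the investigator has to set the rule aside or apply it against some substitute that the protocol does not define. In a multicenter trial, sites need not choose the same way.

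The same sentence leaves two further points open. It does not say which measurement the fall is counted from, and it does not say whether 10% is a proportion of that measurement or a difference in percent-predicted points.

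**Working it through.** The plan gives no figure to reproduce. The check is a comparison of texts, followed by short arithmetic on the scale.

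**1. Variable needed against variables listed (section 8.1.2.9)**

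| Domain in the stated purpose | Listed items |
|---|---|
| Lung volume and capacity | VC, FRC, total lung capacity, FVC |
| Rate of flow | FEV, FEF, PEFR |
| Gas exchange | none |

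The placing of individual items between the first two rows does not affect the result. Seven items are listed, and none of them measures gas exchange. The variable the rule needs, DLCO, is not among them.

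**2. Does another section supply it?**

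DLCO occurs once in the document, in the rule itself. The flow chart and section 8.1.6.1.1 refer only to lung function tests as a group. The joined FEF and PEFR entries look like a text-extraction effect, and nothing suggests that a DLCO line was lost there.

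**3. Can the value be obtained later?**

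The only scheduled test is before Day 1 of Cycle 1. Every later test follows a clinical indication, so it falls after exposure. If DLCO is not recorded at screening, the protocol provides no other pre-treatment opportunity.

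**4. What the unstated scale does**

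Let B be the baseline DLCO in percent predicted. The documents give no DLCO values, so the B values below are assumptions chosen to show a range.

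- Relative reading: the rule triggers below 0.90 × B.
- Percentage-point reading: the rule triggers below B − 10.
- Gap between the two cut-offs: 0.90 × B − (B − 10) = 10 − 0.10 × B.

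| Assumed B | Relative | Points | Gap |
|---|---|---|---|
| 50 | 45 | 40 | 5 |
| 70 | 63 | 60 | 3 |
| 90 | 81 | 80 | 1 |

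Example: with B = 70 and a repeat value of 61, the fall is 9 points. The relative fall is 9/70 = 12.9%, which exceeds 10%. The point fall of 9 does not exceed 10. The same subject meets the rule on one reading and not on the other. The readings agree at B = 100 and diverge further as baseline function worsens.

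**The case against.** The strongest reply is that the section already says baseline testing covers gas exchange, and DLCO is the only gas-exchange variable it uses. On that reading the baseline is intended and the list is merely incomplete. The case report form and Procedure Manual are not part of the documents and may capture DLCO. The rule also leaves room for judgement, since another obvious explanation overrides it. Finally, a fall mentioned in a paragraph that opens with baseline tests is most naturally read as relative to baseline.

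Much of this stands. It shows that the section conflicts with itself, not that the protocol forbids or forgets the measurement. It does not close the gap. A general statement of purpose makes a baseline DLCO possible, whereas the list is what tells a site which values to record. The override for other causes applies only after a fall has been computed. The natural reading of the comparator is plausible, but it is not written down, and it does not settle the scale.

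A reader might go further in three directions that the documents do not support.

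- **That the entry exclusion also fails.** Exclusion 9 in section 5.1.3 reads "Has evidence of interstitial lung disease or active, non-infectious pneumonitis". It sets no DLCO threshold and no change from a reference value. It can be judged on other evidence, and a single screening test could not show a decrease in any case.
- **That dose holds or escalation depend on this rule.** The pneumonitis rows of Table 3 act on toxicity grade. No section ties the DLCO sentence to a hold, a discontinuation, the stopping rules or the escalation decision.
- **That every subject will lack a baseline, or that a reported adverse event rate will be off by a known amount.** The gas-exchange wording means that some or all sites may measure DLCO. The documents give no basis for a count or for a resulting shift in any safety proportion.

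**Conclusion.** The concern holds for the on-study rule. Purpose, rule and collection list in section 8.1.2.9 do not agree, and the pre-treatment DLCO that the rule requires is not secured. Where it is not recorded at screening, the rule cannot be computed later.

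The size in subjects cannot be stated. For the unstated scale, the two readings differ by 1 to 5 percent-predicted points over assumed baselines of 90 down to 50, which is enough to class an individual subject differently.

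The conclusion rests on two assumptions: that the list in the supplied text is complete, and that the unseen case report form and Procedure Manual do not already add DLCO. If they do, what remains is to align the protocol text and to state the comparator and scale. This is an inconsistency worth correcting, not a threat to the design as a whole.

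**What to change.** Reconcile the three parts of section 8.1.2.9:

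1. Add DLCO to the values to be collected and to the screening page of the case report form.
2. State that any repeat DLCO is compared with the subject's own screening DLCO.
3. Have the sponsor state whether the existing 10% is a relative fall or a fall in percent-predicted points. Which one applies is the sponsor's clinical decision, and this review does not propose a cut-off.

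No change to exclusion 9 is needed. The cost is amendment wording and one form field. Baseline lung function testing that covers gas exchange is already an intended screening procedure, so no visit is added. For subjects already treated without a recorded DLCO, the amendment cannot supply the missing value, and they should be identified as not assessable by this rule.
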